Appendix E: Participating Investigators and Institutions

A complete list of participating investigators and institutions will be provided under separate cover.

Medtronic Business Restricted

Appendix F: Ethics Committee and Competent Authority List

A complete list of participating Regulatory Bodies, Competent Authorities, and Ethics Committees and their Chairperson(s) that will be utilized as part of the study will be distributed under separate cover, upon request.

Medtronic Business Restricted

Appendix G: Previous Clinical Investigations

A complete bibliography and summary of relevant literature, summary and results of preclinical testing, and summary of results of previous clinical investigations is provided in the Investigator's Brochure.

Medtronic Business Restricted

Appendix H: Chronic Defibrillation Testing Protocol

If a chronic defibrillation test is performed per physician discretion, the following chronic defibrillation protocol is recommended. When the chronic defibrillation test protocol has been followed, it's considered to have passed chronic defibrillation testing criteria. Specifically, each subject will be induced to produce up to two episodes of SSVA and allowed two shock attempts to convert each SSVA from the EV ICD, for up to a total of 4 potential shocks from the EV ICD (see Figure 9). Starting therapy polarity is at the discretion of the physician (in the programmed setting).

[figure not shown]

Figure 9: Diagram outlining the process of chronic SSVA induction and defibrillation testing

Episode 1

Program Rx1 and Rx2 therapies as follows:

	Rx1	Rx2
NID	30/40	NA
Redetect NID	NA	9/12
VF Therapy Status	ON	ON
Energy	30J	40J
Pathway	As programmed	As programmed

Medtronic Business Restricted

EV ICD Japan Study Clinical Investigation Plan

MDT22010

Version 3.0, 17-OCT-2022

Page 140 of 142

Medtronic

If Episode 1, Rx1 or Rx2 is successful in terminating the episode, the EV ICD System will have passed chronic defibrillation testing criteria. No additional inductions are required, and it is recommended to leave the system implanted with no changes.

Episode 2

	Rx1	Rx2
NID	9/12	NA
Redetect NID	NA	9/12
VF Therapy Status	ON	ON
Energy	40J	40J
Pathway	Opposite of programmed	Opposite of programmed

If Episode 2, Rx1 or Rx2 is successful in terminating the episode, the EV ICD System will have passed chronic defibrillation testing criteria. No additional inductions are required, and it is recommended to leave the system implanted with no changes.

If both Rx1 and Rx2 fail in Episode 2, the EV ICD System will have failed chronic defibrillation testing criteria and the next steps are at the physician's discretion. Medtronic recommends EV ICD device or lead revision (at a minimum), or system removal.

Prior to inducing and throughout the chronic defibrillation protocol, it is recommended to consider the following to improve defibrillation outcome or troubleshooting in the event of failure of first episode(s):

- Check for/resolve high impedance values
- Check for/resolve air in tunnel (e.g., fluoroscopy)
- Check for/resolve gastric bubbles (gas)
- Press on device pocket during testing
- Perform defibrillation during held end tidal expiration (end expiration apnea)

Medtronic Business Restricted

3.0	
Deleted "UADE" and UADE related descriptions overall.Updated section 3.1 "Background" to add status of the EV ICD Pivotal Study.Updated section 5.1 "Duration".Updated section 8.11 "CareLink Transmissions" to have a consistency with the current situation.Updated ISO14155 definition in section 10.3 "Adverse Events and Device Deficiency Definitions" from 2011 to 2020.Updated Appendix D to update the status of EV ICD Pilot and Pivotal Study.	[name] Sr Clinical Research Specialist

Medtronic Business Restricted

2. List of Abbreviations and Definitions of Terms

Abbreviation	Definition
AE	Adverse Event
ATP	Antitachycardia pacing
CEC	Clinical Events Committee
CIP	Clinical Investigation Plan
DMC	Data Monitoring Committee
EV ICD	ExtraVascular Implantable Cardioverter Defibrillator
MHLW	Ministry of Health, Labour, and Welfare
ICD	Implantable Cardioverter Defibrillator
PHD	Pre-hospital Discharge Visit
SAP	Statistical Analysis Plan
S-ICD	Subcutaneous Implantable Cardioverter Defibrillator
SSVA	Sustained shockable ventricular arrhythmia

3. Introduction

This Statistical Analysis Plan (SAP) has been designed to document, before data are analyzed, the rationale for the study design, and the planned analyses that will be included in study reports. This SAP does not limit the analysis in reports. Additional analysis of the study data beyond this plan may be needed. This SAP is developed for the EV ICD Japan study, based on the Clinical Investigation Plan (CIP) version 3.0 dated October 17, 2022.

Today, implantable cardioverter defibrillator (ICD) therapy is the treatment of choice for subjects who are at risk for sudden cardiac death due to life-threatening ventricular arrhythmias. Traditional ICD systems with transvenous leads are considered standard of care for primary or secondary prevention of tachyarrhythmic death. However, these systems have limitations. Short- and long-term complications arising from ICD systems with transvenous leads, such as infection, pneumothorax, venous thrombosis, lead dislodgement, lead malfunction, and lead perforation, have persisted for decades as impediments

to ICD usage. As a result, there is demand for novel ICD systems that circumvent the potential disadvantages of transvenous ICD systems by preserving the heart and vasculature.

Medtronic has developed an extravascular ICD system which uses a substernal lead rather than a transvenous or a subcutaneous lead. The EV ICD System has similar capabilities to a single-chamber transvenous system while avoiding leads in the heart or vasculature. Compared to current market-released non-transvenous subcutaneous ICDs, the EV ICD System includes a smaller device that uses less defibrillation energy which may result in longer battery life and has the additional capabilities to deliver pacing therapies such as antitachycardia pacing (ATP) and backup asystole pacing from a single device.

In order to develop and evaluate a newly designed system for the substernal space, Medtronic completed pre-clinical research evaluations of substernal defibrillation, pacing, and sensing, and subsequently initiated three acute human clinical research feasibility studies with combined 121 implants to explore the potential development of a future chronic implantable extravascular defibrillation system with a lead implanted in the substernal space. Later, a first-in-human chronic pilot study was initiated based on the assurance from acute feasibility data. The acute feasibility and pilot studies contributed to the advancement of the EV ICD program, including refinement of the device, algorithm and implant procedure. Based on the results of this pilot study, a pivotal study with 356 enrollments with 316 subjects with an EV ICD implant procedure attempt was conducted to demonstrate the safety and efficacy of the EV ICD system: a complete single-chamber extravascular ICD system with the lead implanted substernally. Results of this study showed both primary endpoints were met; the defibrillation testing success rate at implant was 98.7% and the freedom from major complications related to the system and/or procedure at 6 months post-implant was 92.6%. At the time of this protocol being written, patients are still in follow-up and the study is undergoing regulatory review.

The EV ICD Japan study aims to supplement the pivotal analysis and provide additional data to support the safety and efficacy of the EV ICD system within a Japanese population.

4. Study Objectives

4.1 Primary Objectives

The first primary objective is to characterize the freedom from major complications related to the EV ICD System and/or procedure at 2 weeks post-implant. The endpoint is defined as a subject's first occurrence of a major complication related to the EV ICD System and/or procedure, as determined by an independent Clinical Events Committee (CEC), that occurs on or prior to 2 weeks (14 days) post-implant. For an adverse event to meet the endpoint, the event must have occurred within 14 days (inclusive) of the EV ICD System implant and be adjudicated by the CEC as being a major complication related (causal relationship) to the EV ICD System and/or procedure. Major complications are those complications resulting in:

- Death
- Permanent loss of defibrillation function (specifically shock) due to mechanical or electrical dysfunction of the device
- Hospitalization
- Prolongation of an existing hospitalization by at least 48 hours
- System revision (reposition, replacement, explant)

The second primary objective is to characterize the defibrillation efficacy at implant of the EV ICD System. The endpoint, defibrillation testing success, is defined as:

- Single sustained shockable ventricular arrhythmia (SSVA) conversion at 20J, or
- Conversion of two consecutive episodes of SSVA at 30J in final system configuration.

Notes:

- In one of the two consecutive SSVA episodes, up to two 30J shocks are permitted.
- To achieve final system configuration, changing the position of the ICD generator and/or the lead, or changing shock polarity is permitted.
- Subjects can return for testing on another day if testing is not fully completed on the day of implant.
- If SSVA cannot be induced, the EV ICD System must be removed (refer to CIP section 8.5.8).
- For more information on the rationale behind these objectives, refer to section 7.7 (i.e., CIP section 12).

implant; but any previously scheduled implant procedures will be allowed to occur. There are no hypotheses for both primary safety and efficacy objectives in this study. The sample size is not pre-specified to satisfy any statistical requirements, but rather to allow for multiple investigational sites enrolling patients and implanting the EV ICD system.

7. Statistical Methods

The CIP version 3.0 dated October 17, 2022 is the currently approved version as of the approval date of this document. Should there be any additional CIP updates, the impacts of it on the integrity of the study will be evaluated; if such impacts are confirmed, the data collected before and after the amendment will be analyzed statistically per ISO 14155:2020 to assess the effect of the amendment on the safety and efficacy analysis.

7.1 Study Subjects

7.1.1 Disposition of Subjects

This is a single-arm study. After subjects sign the informed consent form, they are enrolled in the study. Screening logs are not used in this study as historically they have typically been found to have poor compliance. Extensive inclusion/exclusion criteria have been chosen in this study to restrict the target population to those thought to be best served by this EV ICD system and mitigate the risk of selection bias. Enrollment can be a stand-alone visit or can occur on the same day as the baseline visit. After that, subjects will undergo implant of the EV ICD system, with required defibrillation, sensing, impedance and pacing testing. Subjects will then return for follow-up visits at 2 Weeks, 3 Months, 6 Months, and every 6 months thereafter. Subject disposition will be presented using a flow diagram where completed visits, missed visits, and attrition due to exit and death will be indicated.

7.1.2 Clinical Investigation Plan (CIP) Deviations

A study deviation is an event within a study that did not occur according to the CIP or the Clinical Trial Agreement. Study deviations will result in corresponding Study Deviation eCRFs being completed. These deviations will be summarized with descriptive statistics including, for each type of deviation, how many occurrences there were in the study, and the number of subjects experiencing each type of deviation. Inclusion/exclusion violations will not result in subjects being excluded from analysis of objectives. Of particular importance will be required testing not completed at implant or follow-up. If it is discovered there were subjects not meeting the inclusion/exclusion criteria who underwent an implant attempt and possibly defibrillation testing, additional analyses may be performed with these subjects excluded.

7.1.3 Analysis Sets

All subjects with an implant attempt of the investigational product will be included in the primary analysis for the primary safety objective. All subjects who complete the defibrillation protocol will be included in the primary analysis for the primary efficacy objective.

7.2 General Methodology

Data analysis will be performed by Medtronic statisticians or designees.

The cohort will include all enrolled subjects who undergo the study procedures unless the subject does not complete the required testing, and there are no pre-specified subgroups for assessment. For endpoints involving only measurements collected at follow-up visits, only subjects who complete those visits will be included in the analysis of those endpoints.

7.3 Handling of Missing, Unused, and Spurious Data and Dropouts

All available data will be included in the data listings and tabulations. With regard to the primary safety objective, subjects who exit the study prior to experiencing a major system or procedure-related complication will be censored at the date of their exit (in the case of the subject being lost to follow-up or death of unknown classification, the subject will be censored at the date of last contact with the subject) in the calculation of any Kaplan-Meier freedom from complication rates.

7.4 Adjustments for Multiple Comparisons

There is no adjustment for multiple comparisons. Because a subject may be included in the analysis for the primary safety objective but not the efficacy objective if the subject does not complete the defibrillation protocol, the primary safety and efficacy objectives are not independent.

7.5 Demographic and Other Baseline Characteristics

Descriptive statistics will be used to summarize baseline and demographic characteristics. For categorical data, counts and percentages will be employed, while for continuous variables, means, standard deviation, quartiles, minimum, and maximum will be provided. These statistics will be provided both for all enrolled subjects and for the subset of subjects who undergo implant of the EV ICD system.

7.6 Treatment Characteristics

Descriptive statistics will be used to summarize all implant procedure information collected, including:

- Pre-procedure and substernal tunnel characteristics
- Sensing testing via analyzer and lead insertion
- Closure characteristics
- Operative time: Time of first incision to time of final device pocket suture

7.7 Evaluation of Objectives

7.7.1 Primary Objective #1: Safety

Characterize the freedom from major complications related to the EV ICD System and/or procedure at 2 weeks post-implant.

7.7.1.1 Hypothesis

There are no hypotheses for this objective.

7.7.1.2 Performance Requirements and Endpoint Definition

Performance requirements are not pre-specified for this objective. The endpoint is defined as a subject's first occurrence of a major complication related to the EV ICD System and/or procedure as determined by the independent Clinical Event Committee (CEC) that occurs on or prior to 2-weeks (14-days) post-implant.

For an adverse event to meet the endpoint, the event must have occurred within 14 days (inclusive) of the EV ICD System implant attempt and be adjudicated by the CEC as being a major complication related (causal relationship) to the EV ICD System and/or procedure. Major complications are those complications resulting in:

- Death
- Permanent loss of defibrillation function due to mechanical or electrical dysfunction of the device
- Hospitalization (see CIP Table 10 for Hospitalization definition)
- Prolongation of an existing hospitalization by at least 48 hours
- System revision (reposition, replacement, explant)

7.7.1.3 Rationale for Performance Criteria

This objective is for the purpose of gathering data pertaining to device safety over the first 2 weeks post-implant. There are no pre-specified performance criteria.

7.7.1.4 Analysis Methods

Results will be summarized in aggregate using descriptive statistics. The total number of major complications experienced by subjects for whom an implant is attempted will be summarized. The primary analysis for primary safety endpoint will be based on the endpoint definition described in section 7.7.1.2. Subjects not experiencing an event will be censored at their last point of contact. The 14-day freedom from major complication rate will be generated using the Kaplan-Meier method.

If any adverse events that occurred within 14 days (inclusive) of the EV ICD System implant attempt were adjudicated by the CEC as being major complications and the relatedness to the EV ICD System and/or procedure was determined by the CEC as "probable", a sensitivity analysis will be conducted with such adverse events included as having met the primary safety endpoint. An additional sensitivity

analysis may be performed including major complications with a system or procedure-relatedness classification of “possible”, should there be any such major complications.

7.7.1.5 Determination of Subjects/Data for Analysis

All subjects with an implant attempt of the investigational product will be included in the analysis.

7.7.2 Primary Objective #2: Efficacy

Characterize the EV ICD defibrillation testing success rate at implant.

7.7.2.1 Hypothesis

There are no hypotheses for this objective.

7.7.2.2 Performance Requirements and Endpoint Definition

Performance requirements are not pre-specified for this objective. The endpoint, defibrillation testing success, is defined as:

- Single SSVA conversion at 20J, or
- Conversion of two consecutive episodes of SSVA at 30J in final system configuration.

Notes:

- In one of the two consecutive SSVA episodes, up to two 30J shocks are permitted.
- To achieve final system configuration, changing the position of the ICD generator and/or the lead or changing shock polarity is permitted.
- Subjects can return for testing on another day if testing is not fully completed on the day of implant.

7.7.2.3 Rationale for Performance Criteria

This objective is for the purpose of gathering data pertaining to defibrillation efficacy at implant. There are no pre-specified performance criteria.

7.7.2.4 Analysis Methods

Results will be summarized in aggregate using descriptive statistics. Subjects will be partitioned by the results of their defibrillation testing (e.g., no rescue shocks required, one rescue shock required), with counts and percentage falling into each subgroup reported. Each subject who completes the defibrillation protocol will be determined to either have successfully met the defibrillation endpoint or not met the endpoint. The proportion of subjects having EV ICD defibrillation success at implant will be calculated: the denominator is the number of subjects who complete the defibrillation protocol, and the numerator is the number of subjects who have defibrillation success at implant. Subjects who do not complete the defibrillation protocol will not be included in this primary analysis.

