8.5.7. Induction and Defibrillation Testing

To ensure subject safety in an ambulatory setting, sustained shockable ventricular arrhythmia (SSVA) induction and defibrillation testing is required at implant. Adjust device programming to ensure adequate safety margins for sensing and defibrillation during SSVA induction testing.

The testing protocol may require up to six successful SSVA episodes induced and up to 10 EV ICD shocks delivered (Figure 7).

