8.5.8. Subject Exit for Incomplete Implant Visit

The subject shall be exited if any of the following occur during the implant visit:

- Incomplete Placement of Lead and/or Device – The EV ICD System is not fully implanted.

^{xvi} Lead revision is not permitted if the subject has resumed anticoagulation. Post-procedure anticoagulation should be resumed as soon as possible unless clinically contraindicated (e.g., effusion observed) in subjects who have had atrial fibrillation for ≥ 48 hours in duration prior to the implant procedure and who convert to sinus rhythm during defibrillation testing to diminish the risk of peri-procedural stroke.

Medtronic Business Restricted

- Incomplete Defibrillation Testing Protocol – The subject cannot complete the entire defibrillation testing protocol because they were not inducible or failed to induce a sufficient number of episodes.
 - Note: If the subject completes the initial implant procedure without completing the defibrillation testing protocol, the subject may be brought back prior to hospital discharge to complete the remainder of the defibrillation testing protocol, as outlined in Figure 7.
- Failure of Defibrillation Testing Protocol – The subject completes the defibrillation testing protocol but does not meet the criteria for success for defibrillation testing.
- Inadequate Sensing – The subject cannot achieve an R-wave ≥ 1 mV for the Ring1-Ring2 sensing vector after troubleshooting methods are exhausted.
- Inadequate SSVA Detection – The subject cannot achieve successful VF detection in a single SSVA episode in the Ring1-Ring2 configuration at a value greater than or equal to 0.2 mV after troubleshooting methods are exhausted.

If the subject does not complete the implant visit due to any of the reasons specified above, the EV ICD System shall be explanted, and the subject shall be followed and assessed for AEs through 30 days or until procedure or system related AEs have been resolved, at which point the subject can be exited (see section 8.19). If the subject receives an alternative system (e.g., S-ICD or TV ICD), any AEs related to the alternate system will be recorded during the course of subject participation, but will not be considered related to the EV ICD System.

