Incomplete placement of the lead and/or device, and incomplete or failed electrical or defibrillation testing (including prolongation of hospital stay by allowing time to minimize transient factors affecting defibrillation) are not considered adverse events; however, any adverse events occurring during an unsuccessful implant attempt (e.g., subject allergy to electrodes used during implant) must be recorded and classified on an AE eCRF. Unsuccessful EV ICD system implants and/or failed defibrillation testing shall be evaluated for reporting as a device deficiency.

If the EV ICD System is explanted or repositioned after initial implant procedure but prior to pre-hospital discharge, this shall be captured on a System Modification eCRF.

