Complication	
An adverse event that includes the following is considered a complication:
 
 • Results in death, • Involves any termination of significant device function (i.e., defibrillation therapy), or • Requires an invasive intervention 
Non-invasive (21 CFR 812.3(k)): when applied to a diagnostic device or procedure, means one that does not by design or intention:
 
Penetrate or pierce the skin or mucous membranes of the body, the ocular cavity, or the urethra, or enter the ear beyond the external auditory canal, the nose beyond the nares, the mouth beyond the pharynx, the anal canal beyond the rectum, or the vagina beyond the cervical os.
 
For purposes of this part, blood sampling that involves simple venipuncture is considered non-invasive, and the use of surplus samples of body fluids or tissues that are left over from samples taken for non-investigational purposes is also considered non-invasive.
 
Note: Only system or procedure related AEs will be classified as complication (major, minor) or observation.

Major complication	
A system or procedure-related complication which results in:
 
 • Death • Permanent loss of defibrillation function due to mechanical or electrical dysfunction of the device • Hospitalization • Prolongation of an existing hospitalization by at least 48 hours • System revision (reposition, replacement, explant) 
Note: Only system or procedure related AEs will be classified as complication (major, minor) or observation.

Minor complication	
Any complication that is not a major complication (e.g., event classified as a complication solely based on intravenous drug administration).
 
Note: Only system or procedure related AEs will be classified as complication (major, minor) or observation.

Observation	
Any adverse event that is not a complication.
 
Note: Only system or procedure related AEs will be classified as complication (major, minor) or observation.

Timing	
Pre-Implant Procedure	Occurs after the IC has been signed but before the skin incision during the EV ICD implant procedure.

Medtronic Business Restricted

EV ICD Japan Study Clinical Investigation Plan

MDT22010

Version 3.0, 17-OCT-2022

Page 90 of 142

Medtronic

During Implant Procedure	Occurs during the EV ICD implant procedure, after skin incision and prior to completion of skin closure.	

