7.7.2.5 Determination of Subjects/Data for Analysis

All subjects who complete the defibrillation protocol will be included in the analysis.

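### No planned rate counts implant attempts that end in explant without completed defibrillation testing as non-successes, and the 20J limb of the endpoint is not aligned with the final-configuration requirement

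*SAP*

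**What the plan says.** **Denominator.** SAP 7.7.2.5 defines the efficacy set: "All subjects who complete the defibrillation protocol will be included in the analysis". SAP 7.7.2.4 adds the converse: "Subjects who do not complete the defibrillation protocol will not be included in this primary analysis". SAP 7.1.3 and CIP 12.4.4 and 12.4.5 agree. The safety set is wider, being all implant attempts, and SAP 7.4 acknowledges that "a subject may be included in the analysis for the primary safety objective but not the efficacy objective".

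**What happens to non-completers.** CIP 8.5.8 requires explant and exit when placement is incomplete, when sensing or detection is inadequate, when testing is failed, or when testing cannot be finished "because they were not inducible or failed to induce a sufficient number of episodes". The same section says of "Incomplete placement of the lead and/or device, and incomplete or failed electrical or defibrillation testing" that they are not adverse events. CIP 10.3 (Table 10) notes: "Only system or procedure related AEs will be classified as complication (major, minor) or observation".

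**Stopping rule.** CIP 12.2 and SAP 6 stop enrollment at 15 completers of defibrillation testing, although implants already scheduled may go ahead.

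**Endpoint wording.** The first limb in SAP 7.7.2.2 reads "Single SSVA conversion at 20J, or" and carries no further condition. Only the second limb, two consecutive conversions at 30J, is tied to the final system configuration. CIP 8.5.7.2 requires success to be shown again once the device or lead has been moved. CIP 8.5.7.3 requires both detection success and defibrillation success in the final configuration, without separating 20J from 30J.

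**The concern.** The study exists to characterize acute safety and performance of a novel system and procedure in Japanese patients. A reader will want to know how often an implant attempt ends with a tested system in place, and the completer rate does not answer that. Absent a separate adverse event, a subject explanted without completing testing is outside the efficacy rate and has no event in the safety rate. Because the stopping rule counts completers, that subject is followed by another, and the reported proportion does not register the attempt.

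The exclusion may also depend on outcome. By the endpoint text, a 20J conversion needs one induced episode, while a 20J failure needs at least two more. CIP 8.5.7 says: "The testing protocol may require up to six successful SSVA episodes induced". A subject whose early shocks fail therefore has more opportunities to leave the denominator for want of inducible episodes.

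On the endpoint wording, a 20J conversion obtained before the lead or device is moved can be scored in more than one way, depending on which section is read.

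**Working it through.** **1. The documents' own precedent.** CIP 3.1 gives the pilot study: 21 implant procedures, 20 subjects with testing completed, 18 successes.
- Among completers: 18/20 = 90.0%, which reproduces the stated figure.
- Per attempt: 18/21 = 85.7% (exact 95% CI 63.7 to 97.0).

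The gap is 4.3 points from one untested subject. The documents do not say why that subject was untested, and the pilot may have used a different test protocol. It shows only that the two rates can diverge at this sample size.

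**2. This trial.** The documents give no expected number of non-completers, so k is assumed. Per-attempt rate = successes / (15 + k), with exact (Clopper-Pearson) 95% intervals:

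| Completers successful | Planned rate | k | Per-attempt rate |
|---|---|---|---|
| 15/15 | 100% (78.2 to 100) | 1 | 15/16 = 93.8% (69.8 to 99.8) |
| 15/15 | 100% | 2 | 15/17 = 88.2% (63.6 to 98.5) |
| 15/15 | 100% | 3 | 15/18 = 83.3% (58.6 to 96.4) |
| 14/15 | 93.3% (68.1 to 99.8) | 1 | 14/16 = 87.5% (61.7 to 98.4) |

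In the first three rows the planned rate stays at 100% whatever k is.

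**3. How likely is any gap?** With an assumed non-completion probability q per attempt and independent attempts, the chance of at least one non-completer before the 15th completer is 1 − (1 − q)^15. For q = 2%, 5% and 10% this is 26%, 54% and 79%. It is not the exact chance that the two rates differ: an explant for inadequate detection can separate them with no non-completer, and scheduled implants may continue past 15.

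**4. Outcome dependence, illustration only.** Let i be an assumed, independent chance that a needed episode cannot be induced. Non-completion is 1 − (1 − i)^n, with n = 1 if the 20J shock would succeed and n = 3 as a minimum if it would fail, counting only what the endpoint requires.

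| i | n = 1 | n = 3 |
|---|---|---|
| 2% | 2.0% | 5.9% |
| 5% | 5.0% | 14.3% |
| 10% | 10.0% | 27.1% |

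The direction follows from the endpoint text. The size does not; see the objection.

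**5. The 20J limb.** The text allows this sequence. Detection testing starts on the same Episode 1 as the 20J test (CIP 8.5.7.3). A manually delivered shock counts (CIP 8.5.7.2). If detection fails at both sensitivity settings, the lead is repositioned (CIP 8.5.7.3). Suppose the 20J shock converted on Episode 1, the lead was then moved, and success was not shown again. With 14 other completers, all successful:
- Endpoint text read literally: a success, 15/15 = 100%.
- CIP 8.5.7.2 and 8.5.7.3 applied, scored as not meeting the endpoint: 14/15 = 93.3%.
- Treated as not having completed the protocol: left out, 14/14 = 100%.

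Three scorings of one subject are defensible from the current text.

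**The case against.** The completer set is a deliberate choice, stated identically in both documents, and it matches the objective, which is testing success and not implant success. A non-inducible subject says nothing about whether the shock works. The pilot reported its rate the same way. All of that stands, and it is why the completer rate should remain primary.

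A reader might infer that non-completers disappear from the report. The documents do not support that. The SAP plans a disposition diagram (7.1.1), a deviation summary that singles out required testing not done at implant (7.1.2), an implant-procedure summary (7.6), programs summarizing study exits (section 8) and a device-deficiency listing (7.8), and section 3 allows further analyses. With at most 25 enrolled, individual cases will be visible. What is missing is a rate that counts them.

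A reader might also take the figures in step 4 as an estimate of bias. They are not. They assume independence between episodes, whereas inducibility is plausibly a patient trait, so a subject already induced once may well be induced again. CIP 8.5.7.1 allows other induction methods and attempts on another day before discharge, and CIP 8.5.8 allows a return to finish testing. The figures are probably too high, and without a frequency of 20J failure the net effect cannot be derived.

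On the 20J limb, site conduct is already governed by CIP 8.5.7.2 and 8.5.7.3, and the sequence in step 5 needs a 20J conversion together with two failed detection settings. Figures 7 and 8 are not shown in the text reviewed and may clarify the test flow. This makes the case uncommon, but it does not alter the SAP endpoint wording.

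**Conclusion.** Both parts hold, as a cheap improvement and not as an error in the primary analysis. No planned rate counts an attempted subject explanted without completed testing as a non-success, and the stopping rule in effect makes up for such subjects. With 15 of 15 completers successful, each of the first three such attempts would lower a per-attempt rate by about 5 to 6 points, while the planned rate stays at 100%. The numbers of non-completers are assumed. Outcome-dependent exclusion is possible, but its size cannot be derived from the documents.

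The stronger reading, that the reported success rate is invalid or misleading as defined, is not supported: it is a valid proportion for its stated set. The study has no hypothesis, performance goal or decision rule, so no error rate or conclusion is at risk.

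The endpoint text and the configuration statements must be reconciled. One affected subject among 15 moves the primary rate by up to 6.7 points (100% against 93.3%).

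**What to change.** **1. Supplementary rate (SAP 7.7.2.4 and 7.7.2.5).** Keep the completer proportion as primary. Add one rate, labelled supplementary:
- Denominator: all subjects with an implant attempt.
- Numerator: subjects who meet the defibrillation endpoint, as reconciled under item 2, and have the EV ICD System in place at hospital discharge. Testing finished on a later day before discharge counts.
- Tabulate non-successes by CIP 8.5.8 reason, with non-inducible subjects on a separate line so that inducibility is not read as shock failure.

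The cost is a few sentences and one table from data already collected. The downside is a second figure, equal to or lower than the primary, that mixes implantability with shock efficacy; the label and the breakdown by reason address this.

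**2. Endpoint text.** Reconcile the unqualified 20J limb (CIP Synopsis, 4.1.1, 8.5.7.2 and 12.4.2; SAP 4.1 and 7.7.2.2) with the new- or final-configuration statements in CIP 8.5.7.2 and 8.5.7.3, so that one scoring rule applies when a device or lead is moved after a 20J conversion. List any such subject separately. This review does not say which wording should govern. The cost is a wording change in both documents.
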